7.1.1 Study Procedures

The study procedures and assessments are described in the section below and presented in detail in Section 9.1 (diabetes status assessments), Section 9.2 (safety), Section 9.3 (immunological assessments), Section 9.4 (genetic status assessments), Section 9.5 (vitamin D status), Section 9.7 (Quality of Life) Section 9.7 (pubertal stage, concomitant medication assessments), and Section 9.9 (demographics).

Recording and reporting of AEs are described in detail in Section 11.

The timing of all study events is shown in Table 2 and Table 3 in Section 7.1.

7.1.1.1 All Visits, Visit 1 through Visit 8

Note that the patient should attend all study visits in the morning following an overnight fast (>10 hours, water allowed). For patients with evidence of an infection (including fever), the complete visit should be postponed for 5 days or until the patient has recovered.

7.1.1.2 Timing of all visits, Visit 1 through Visit 8

The first visit, the screening visit (Visit 1) should be performed 14 to 28 days before planned Visit 2 (Baseline), when Vitamin D treatment starts. One month (30 days) later, at Visit 3, the first injection of Diamyd will be administered. For Visit 4 (second Diamyd administration), the visit date must be set in accordance with Visit 3 (i.e. the first Diamyd administration) so that the first and second Diamyd doses will be 30 days apart (± 5 days). For Visit 5 (third Diamyd administration) the visit date must be set in accordance with Visit 4 (i.e. the second Diamyd administration) so that the second and third Diamyd doses will be 30 days apart (± 5 days). For Visit 6, 7 and 8, the visit date must be calculated from baseline (Visit 2) ± 14 days.

7.1.1.3 Visit 1, Screening (Day -14 to -28)

The screening examination will take place within 6 months of diagnosis of T1D. Potential study patients and guardian(s), where applicable, will receive both written and oral information about the study procedures, potential risks, and benefits. Before any study specific procedures may be performed, the patients and guardian(s), where applicable, must sign the informed consent form (ICF). After written informed consent has been obtained, the following activities and assessments will be performed:

- Eligibility will be checked versus the inclusion/exclusion criteria
- Demographics (including age and gender)
- Medical history
- Family history of T1D
- General Physical Examination, including weight and height
- Neurological Assessment
- Concomitant medication
- Vital signs (BP)
- Pubertal stage, if applicable

- Glycemic variability/fluctuations device (FreeStyle LibrePro, FGM) will be given to the patient
- Urine pregnancy test (menarchal females only)
- Blood sampling for hematology, clinical chemistry and GAD65A
- Blood sampling for vitamin D status
- Urine analysis for microalbuminuria and creatinine
- Blood samples for diabetes status (fasting C-peptide, HbA1c and fasting glucose)
- The patient will be instructed to collect the insulin dose 4 days prior to the next visit and the site will send text message/call to remind the patient

If the fasting c-peptide concentration is not $\geq 0,12$ nmol/L (0.36 ng/ml) at the screening visit this test can be repeated on another day within a period of 2 weeks (maximum 2 tests on different days within a 2-week period).

Examinations will be performed according to Table 2, and in the order outlined in the electronic case report form (eCRF).

7.1.1.4 Visit 2, Baseline (Day 1)

At Visit 2 (baseline) the following activities and assessments will be performed:

- Eligibility will be checked versus the inclusion/exclusion criteria
- Randomization in Interactive Web Response System (IWRS)
- Start of treatment with the oral treatment of vitamin D/Placebo (if the Vitamin D serum levels are below 100 nmol/L [40 ng/ml] at screening)
- General Physical Examination, including weight and height
- Neurological Assessment
- Concomitant medication
- Vital signs (BP)
- Insulin dose collected (Exogenous insulin dose/kg/24 hours) for 4 days prior to visit
- AEs
- Urine pregnancy test (menarchal females only)
- Self-reported severe hypoglycemia (defined as needing help from others and/or seizures and/or unconsciousness)
- QoL questionnaire
- MMTT
- Blood sampling for hematology, clinical chemistry and GAD65A
- Blood sampling for other immunological parameters
- Blood sampling for vitamin D status
- Urine analysis for microalbuminuria and creatinine
- Blood samples for diabetes status (fasting C-peptide, MMTT-induced C-peptide, HbA1c, fasting glucose and MMTT-induced glucose)
- Electronic Diary (eDiary) activated and patients trained in how to use it

Examinations will be performed according to Table 2, and in the order outlined in the eCRF.

7.1.1.5 Visit 3, Month 1 (Day 30 \pm 5)

At Visit 3 (Month 1) the following activities and assessments will be performed:

- Treatment with Diamyd/Placebo injection
- Injection site inspection by the Investigator/Study Nurse
- Patient instructed on how to record injection site injections in the eDiary
- General Physical Examination, including weight and height
- Neurological Assessment
- Concomitant medication
- Vital signs
- AEs
- Urine pregnancy test (menarchal females only)
- Self-reported severe hypoglycemia (defined as needing help from others and/or seizures and/or unconsciousness)
- Blood sampling for hematology, clinical chemistry, GAD65A and HLA characterization
- Blood sampling for other immunological parameters
- Blood sampling for vitamin D status
- Urine analysis for microalbuminuria and creatinine
- Blood samples for diabetes status (fasting C-peptide, HbA1c and fasting glucose)
- Check of eDiary use compliance

Examinations will be performed according to Table 2, and in the order outlined in the eCRF.

7.1.1.6 Visit 4, Month 2 (Day 60 ±5) and Visit 5, Month 3 (Day 90 ±5)

For Visit 4 and 5 the visit date must be set in accordance with Visit 3 and 4, respectively, so that the first, second and third doses will be 30 days apart (\pm 5 days).

At Visit 4 (Month 2) and Visit 5 (Month 3) the following activities and assessments will be performed:

- Treatment with Diamyd/Placebo injection
- Injection site inspection by the Investigator/Study Nurse and check for patient reported injection site recordings for previous visit in eDiary
- General Physical Examination, including weight and height
- Neurological Assessment
- Concomitant medication
- Vital signs (BP)
- AEs
- Urine pregnancy test (menarchal females only)
- Self-reported severe hypoglycemia (defined as needing help from others and/or seizures and/or unconsciousness)
- Blood sampling for hematology, clinical chemistry and GAD65A
- Blood sampling for other immunological parameters
- Blood sampling for vitamin D status
- Urine analysis for microalbuminuria and creatinine
- Blood samples for diabetes status (fasting C-peptide, HbA1c and fasting glucose)
- Check of eDiary use compliance

- Confirm with the patient that last dose of vitamin D/placebo will occur at month 4 (before next visit month 6)

Examinations will be performed according to Table 2, and in the order outlined in the eCRF.

7.1.1.7 Visit 6, Month 6 (Day 180 ±14)

At Visit 6 (Month 6) the following activities and assessments will be performed:

- General Physical Examination, including weight and height
- Neurological Assessment
- Concomitant medication
- Vital signs
- Pubertal stage, if applicable
- Glycemic variability/fluctuations device (FreeStyle LibrePro, FGM) will be given to the patient
- AEs
- Urine pregnancy test (menarchal females only)
- Self-reported severe hypoglycemia (defined as needing help from others and/or seizures and/or unconsciousness)
- QoL questionnaire
- MMTT
- Blood sampling for hematology, clinical chemistry and GAD65A
- Blood sampling for other immunological parameters
- Blood sampling for vitamin D status
- Urine analysis for microalbuminuria and creatinine
- Blood samples for diabetes status (fasting C-peptide, MMTT-induced C-peptide, HbA1c, fasting glucose, and MMTT-induced glucose)
- Check of eDiary use compliance
- Collection of used and unused vitamin D/placebo for accountability

Examinations will be performed according to Table 2, and in the order outlined in the eCRF.

7.1.1.8 Visit 7, Month 15 (Day 450 ±14)

At Visit 7 (Month 15) the following activities and assessments will be performed:

- General Physical Examination, including weight and height
- Neurological Assessment
- Concomitant medication
- Vital signs
- Pubertal stage, if applicable
- Glycemic variability/fluctuations device (FreeStyle LibrePro, FGM) will be given to the patient
- AEs
- Urine pregnancy test (menarchal females only)
- Self-reported severe hypoglycemia (defined as needing help from others and/or seizures and/or unconsciousness)
- QoL questionnaire
- MMTT
- Blood sampling for hematology, clinical chemistry and GAD65A

- Blood sampling for other immunological parameters
- Blood sampling for vitamin D status
- Urine analysis for microalbuminuria and creatinine
- Blood samples for diabetes status (fasting C-peptide, MMTT-induced C-peptide, HbA1c, fasting glucose and MMTT-induced glucose)
- Serological test for Covid-19 (for patients completing their Visit 7 after 01 January 2020)
- Check of eDiary use compliance and inactivate the account (only applicable for patients that are not continuing in the Extension Study Period)

Examinations will be performed according to Table 2, and in the order outlined in the eCRF.

7.1.1.9 Visit 8, Month 24 (Day 720 ±14)

Visit 8 will only be performed by patients that are ongoing i.e. have not performed Visit 7 (Month 15) when protocol version 7 is approved, implemented and gives their consent to enter the Extension Study Period. Study patients and guardian(s), where applicable, will be asked to sign the updated ICF describing Visit 8 (Extension Study Period).

At Visit 8 (Month 24) the following activities and assessments will be performed:

- General Physical Examination, including weight and height
- Neurological Assessment
- Concomitant medication
- Vital signs
- Pubertal stage, if applicable
- Glycemic variability/fluctuations device (FreeStyle LibrePro, FGM) will be given to the patient
- AEs
- Urine pregnancy test (menarchal females only)
- Self-reported severe hypoglycemia (defined as needing help from others and/or seizures and/or unconsciousness)
- QoL questionnaire
- MMTT
- Blood sampling for hematology, clinical chemistry and GAD65A
- Blood sampling for other immunological parameters
- Blood sampling for vitamin D status
- Urine analysis for microalbuminuria and creatinine
- Blood samples for diabetes status (fasting C-peptide, MMTT-induced C-peptide, HbA1c, fasting glucose and MMTT-induced glucose)
- Serological test for Covid-19
- Check of eDiary use compliance and inactivate the account

Examinations will be performed according to Table 3, and in the order outlined in the eCRF.

7.2 Patient Diary

The patients will be supplied with an eDiary at Visit 2. The diary will be internet based and the patients will be able to access the diary from either a computer or a smart phone. From Visit 3 until Visit 8 the patient will record insulin doses 4 days before each visit (at Visit 2 the insulin dose will be collected at the visit and will be done by the Investigator and recorded in the eCRF). The patient will also use the eDiary for documentation of injection site reactions during the week following injection (Visits 3, 4 and 5), starting the day after the injection.

The patient will be carefully instructed by study personnel on how to log in and complete the eDiary. The investigator/study nurse will review the eDiaries at each visit to check that the patient is completing the eDiary as instructed. Injection site reactions reported by patients in the eDiary during day 1-7 following an injection should not be reported as AEs in the eCRF.

7.3 Study Stopping Criteria

The Sponsor and the investigators reserve the right to discontinue the study at any time for safety reasons or other reasons jeopardizing the justification of the study. Such a termination will be implemented in a time frame that is compatible with the patient's wellbeing.

If the study is prematurely terminated or suspended, the investigator should promptly inform the patients and assure appropriate therapy and follow-up. The Sponsor will notify the Regulatory Authorities and the Independent Ethics Committees (IECs) of any plans to terminate the study.

7.4 Decision Criteria

A patient is included in the study when the ICF has been signed at the screening visit (Visit 1). No patients will be enrolled until approvals from the appropriate IECs and Regulatory Authorities have been obtained.

Prior to the study starting, it will be confirmed that all regulatory requirements for starting the study are met. All key documents must be on file in the Sponsor and Investigator's File, respectively.

7.5 Management of the Disease

All patients will continue to receive intensive insulin treatment through their personal physicians via multiple daily injections of insulin or via insulin pump and should not use any oral or injected non-insulin pharmaceuticals for glycemic control. If, by mistake, such medication is introduced during the study, this is not a reason for discontinuation of the patient. The primary responsibility for diabetes management will be the treating or referring diabetes care provider, but the research study team will provide close additional support through interaction by phone as needed. Diabetes management will be monitored by the study staff with phone calls between study visits as needed. Patients will fill in their insulin doses 4 days before each visit in the patient diary.

The following diabetes treatment goals will be given to patients and treating physicians in accordance with the current recommendations of the American Diabetes Association (ADA) ²⁷

- Pre-meal glucose 4.4 to 7.2 mmol/L
- Bedtime/overnight glucose 5 to 8.3 mmol/L
- HbA1c <53 mmol/mol (Diabetes Control and Complications Trial [DCCT]-aligned)

These goals are only for guidance and are not considered as violating the protocol if not achieved, but it is regarded as important that every patient and treating physician make their best effort to achieve these recommendations.

The investigator/diabetes team/study nurse will provide support for T1D management by making scheduled phone calls to patients if HbA1c results are ≥ 53 mmol/mol at any study visit.

7.6 Data Safety Monitoring Board

An independent DSMB will be appointed. The DSMB will review the safety data throughout the study period twice a year. A DSMB charter will be written to outline the working procedures and the duties of the DSMB.

8 STUDY POPULATION

Approximately 22 sites in Sweden, Spain, Czech Republic and the Netherlands will include up to 106 patients. T1D patients, diagnosed within 6 months are given information about the study and they (and their guardian(s) if applicable) are asked to participate in the trial.

8.1 Inclusion Criteria

1. Informed consent given by patients and/or patient's parent(s) or legal acceptable representative(s) (guardian(s)) according to national regulations
2. T1D according to the ADA classification diagnosed ≤ 6 months at the time of screening
3. Age: ≥ 12 and < 25 years old
4. Fasting C-peptide ≥ 0.12 nmol/L (0.36 ng/ml) on at least one occasion (maximum 2 tests on different days within a period of 2 weeks)
5. Positive for GAD65A but $< 50\,000$ IU/ml
6. Females must agree to avoid pregnancy and have a negative urine pregnancy test.

Patients of childbearing potential must agree to use adequate contraception, until one (1) year after the last administration of Diamyd. Adequate contraception is as follows:

For females of childbearing potential:

- a. oral (except low-dose gestagen (lynestrenol and norethisteron)), injectable, or implanted hormonal contraceptives
- b. combined (estrogen and progestogen containing)
- c. oral, intravaginal or transdermal progesterone hormonal contraception associated with inhibition of ovulation
- d. intrauterine device
- e. intrauterine hormone-releasing system (for example, progestin-releasing coil)
- f. bilateral tubal occlusion
- g. vasectomized male (with appropriate post vasectomy documentation of the absence of sperm in the ejaculate)
- h. male partner using condom
- i. abstinence from heterosexual intercourse

For males of childbearing potential:

- a. condom (male)
- b. abstinence from heterosexual intercourse

8.2 Exclusion Criteria

1. Previous or current treatment with immunosuppressant therapy (although topical or inhaled steroids are accepted)
2. Continuous treatment with anti-inflammatory drug (sporadic treatment e.g. because of headache or in connection with fever a few days will be accepted)
3. Treatment with any oral or injected anti-diabetic medications other than insulin
4. Treatment with Vitamin D, marketed or not, or unwilling to abstain from such medication during the trial

5. A history of anemia or significantly abnormal hematology results at screening
6. A history of epilepsy, head trauma or cerebrovascular accident, or clinical features of continuous motor unit activity in proximal muscles
7. Clinically significant history of acute reaction to vaccines or other drugs in the past
8. Treatment with any vaccine, including influenza vaccine, within 4 months prior to planned first study drug dose or planned treatment with any vaccine up to 4 months after the last injection with study drug.
9. Participation in other clinical trials with a new chemical entity within the previous 3 months
10. Inability or unwillingness to comply with the provisions of this protocol
11. A history of alcohol or drug abuse
12. A significant illness other than diabetes within 2 weeks prior to first dosing
13. Known HIV or hepatitis
14. Females who are lactating or pregnant (the possibility of pregnancy must be excluded by urine β HCG on-site within 24 hours prior to the Diamyd/placebo treatment)
15. Presence of associated serious disease or condition, including active skin infections that preclude intralymphatic injection, which in the opinion of the investigator makes the patient non-eligible for the study
16. Deemed by the investigator not being able to follow instructions and/or follow the study protocol

8.3 Recruitment and Screening

Eligible patients and/or their parent(s)/legal guardian(s) will have the study explained to them, and will receive the written patient information. After having had the time to review the nature of the study, they will have the opportunity to ask questions to the investigational team. If, after this, the patients agree to participate, they will personally sign and date the written ICF. Patients and/or their parent(s)/legal guardian(s) will provide written informed consent before any study-related procedures are performed.

The patients and/or their parent(s)/legal guardian(s) will then receive a copy of the signed and dated patient information/ICF.

8.4 Patient Withdrawal Criteria

The patient and the parent(s) / legal guardian(s) (where applicable) will receive oral and written information about the study, which includes information about the right to withdraw from the trial at any time without prejudice to future treatment. In addition, the patient may be withdrawn at the investigator's or Sponsor's discretion at any time if regarded in the patient's best interest. In the event that the patient drops out of the trial or is withdrawn from the trial, the appropriate withdrawal page (Study Termination Report) in the eCRF must be completed. Please note that a Study Termination Report must be completed for all patients who have given informed consent and who have been assigned a patient number.

Reasonable efforts should be made to contact any patient lost to follow-up during the course of the trial in order to complete assessments and retrieve any outstanding data.

Patients withdrawn after randomization will not be replaced.

Note that any changes in insulin requirement are not a reason for withdrawal of the patient from the study.

8.5 Patient Withdrawal

In accordance with the Declaration of Helsinki, the investigator must explain to the patient that they have the right to withdraw from the study at any time, and that this will in no way prejudice their future treatment. The reason for any kind of withdrawal must be recorded on the appropriate section of the eCRF.

There will be two main categories for withdrawals from the study:

Complete withdrawal (i.e. stopping investigational product(s) and also continued efficacy and safety evaluations). In order to achieve as complete as possible 15 month follow-up, whenever feasible, patients that are considered for complete withdrawal should be asked if they could consider to return for a 15-month visit, preferable complete visit but as a minimum do the MMTT, C-peptide and HbA1c sampling, and collection of AEs. Attempts should be made to contact patients lost to follow-up with respect to this.

Standard reasons for withdrawing from further participation in the study and from the follow-up visits may be:

- Patient's decision (withdrawal of consent to participate)
- Patient lost to follow-up

Withdrawals from investigational product(s) (i.e. stopping one or several investigational products, but continuing follow-up visits, including efficacy and safety evaluations)

Standard reasons from withdrawing from taking further investigational product, but continuing follow-up visits and safety evaluations may be:

- Unacceptable AEs
- Patient request
- Investigator's discretion
- Patient lost to follow-up/non-attendance
- Intercurrent illness
- The patient becomes pregnant

Diamyd/placebo should not be given to the patient if the patient after inclusion in the study develops/experiences:

- Brain damage, epilepsy, head trauma, neurological disease
- Any active, serious hormonal disease other than T1D
- Other severe autoimmune disease (except celiac disease which is accepted for inclusion)
- Immune-suppressive treatment
- Cancer, cancer treatment
- Any other diabetes drugs other than insulin (and the combination regimen administered in this study)
- Any vaccination

- Drug/alcohol abuse
- Becomes pregnant or is no longer willing to use safe contraceptives during the study

Vitamin D/placebo treatment should not be continued if the patient after inclusion in the study develops/experiences:

- Symptoms of hypercalcemia such as tiredness, euphoria, drowsiness, nausea, weight loss, thirst, polyuria, nefrocalcinosis, renal failure
- Arrhythmia
- Pancreatitis

However, whenever a patient is withdrawn from a study, or for whatever reason is not coming to any further visits, a final study evaluation must be completed for that patient stating the reason(s) why the patient was withdrawn from the study. All documentation concerning the patient must be as complete as possible.

Withdrawals due to non-attendance must be followed up by the investigator to obtain the reason for non-attendance. Withdrawals due to intercurrent illnesses or AEs must be fully documented in the eCRF, with the addition of supplementary information if available and/or appropriate.

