6.4.2 Secondary Endpoints

The key secondary endpoints to evaluate diabetic status are:

- Change in insulin-dose-adjusted HbA1c (IDAA1c) between baseline and 15 months.
- Change in HbA1c between baseline and 15 months.
- Change in daily exogenous insulin consumption between baseline and 15 months.

The other secondary endpoints to evaluate diabetic status are:

- Change in glycemic variability/fluctuations (evaluated from data from continuous glucose monitoring FreeStyle LibrePro, Flash Glucose Monitoring [FGM]) over 14 day period between Screening and 15 months.
- Proportion of patients with $IDAA1c \leq 9$ at 15 months.
- Proportion of patients with a stimulated maximum C-peptide level above 0.2 nmol/L (0.6 ng/ml) at 15 months.
- Proportion of patients with a stimulated 90min C-peptide level above 0.2 nmol/L (0.6 ng/ml) at 15 months.
- Number of self-reported episodes of severe hypoglycemia (Severe hypoglycemia defined as needing help from others and/or seizures and/or unconscious) between baseline and 15 months.
- Change in Rate of hypoglycemic events between baseline and 15 months.

- Number of patients having at least 1 severe hypoglycemic event between baseline and 15 months.
- Change in maximum C-peptide during MMTT between baseline and 15 months.
- Change in Fasting C-peptide between baseline and 15 months.
- C-peptide measured at 30, 60, 90, and 120 minutes during MMTT at 15 months.
- Change in body weight and body mass index (BMI) between baseline and 15 months

The secondary endpoints to evaluate safety are:

- Injection site reactions
- Occurrence of AEs
- Laboratory measurements (hematology and clinical chemistry)
- Urine analysis (microalbuminuria, creatinine)
- Physical examinations, including neurological assessments
- GAD65A titer
- Vital signs (blood pressure [BP])

The secondary endpoints to evaluate the influence on the immune system are:

- Concentrations of serum autoantibodies towards GAD65 and IA-2.
- Concentrations of serum autoantibody isotypes towards GAD65.
- Secretion of cytokines interleukin (IL)-1, IL-2, IL-5, IL-13, IL-10, IL-17, interferon (IFN) γ , and tumour necrosis factor (TNF) α by peripheral blood mononuclear cells (PBMCs) upon stimulation with GAD65.
- Serum concentrations of cytokines IL-1, IL-2, IL-5, IL-13, IL-10, IL-17, IFN γ , and TNF α .
- Secretion of cytokines IL-1, IL-2, IL-5, IL-13, IL-10, IL-17, IFN γ , and TNF α by PBMCs upon stimulation with anti-CD3 and anti-CD28.

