- h. The patient will record injection site reactions in the eDiary starting the day after injection and for 7 days following the injection. Injection site reactions reported by patients in the eDiary during day 1-7 following an injection should not be reported as an AE in the eCRF. Any injections site reactions reported after the 1 week recording period will be recorded as AEs in the eCRF.
- i. Patients will record insulin dose in the eDiary for 4 days prior each visit starting from Visit 2. Insulin dose collected at Visit 2 (for the 4 days prior to Visit 2) will be done by the Investigator and recorded in the eCRF.
- j. FGM during 2 weeks post visit for Visits 1, 6 and 7. Patients will be given instructions on when and where to return the device after the testing period. For instruction on how to return the Freestyle Libre Pro sensor, please refer to the Freestyle Libre Pro Worksheet.
- k. The number of self-reported severe hypoglycemia (defined as needing help from others and/or seizures and/or unconsciousness) should be recorded in the eCRF and each event will be recorded separately.
- l. See Procedure for MMTT in the Operations Manual
- m. Only applicable to patients completing their Visit 7 after 01 January 2020.
- n. Patients that have completely withdrawn from the study will be asked to return for a final visit at month 15, in order to achieve as complete as possible follow-up. See section 8.5 for further details.

Table 3 Schedule of Study Events, Extension Study Period

Event	V8 ^g Month 24
DAY	720 (±14)
General Physical Exam ^a	X
Neurological Assessment	X
Concomitant Medication	X
Vital signs (BP)	X
Pubertal Stage, if applicable ^b	X
eDiary use compliance	X
Insulin Dose Collected ^c	X
FreeStyle LibrePro, FGM ^d	X
AEs	X
Urine Pregnancy Test (menarchal females only)	X
Self-reported severe hypoglycemia ^e	X
QoL questionnaire	X
MMTT ^f	X
Blood Sampling for Safety, Genetics, Vitamin D levels and Immunology:	
Hematology	X
Clinical Chemistry	X
GAD65A titer	X
Vitamin D level	X
Covid-19 serological test	X
Other immunological parameters as specified in Section 6.4.2	X
Urine Analysis:	
Microalbuminuria	X
Creatinine	X
Blood Sampling for Diabetes Status:	
Fasting C-peptide	X
MMTT-induced C-peptide^f	X
HbA1c	X
Fasting Glucose	X
MMTT-induced Glucose^f	X

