13.2.4 Level of Significance, Multiple Comparisons and Multiplicity

The primary endpoint and the key secondary endpoints will be tested hierarchically at the 5% significance level. This implies the following testing sequence:

1. Change in C-peptide $AUC_{\text{mean } 0-120 \text{ min}}$ during a MMTT between baseline and 15 months.
2. Change in IDAA1c between baseline and 15 months.
3. Change in HbA1c between baseline and 15 months.
4. Change in daily exogenous insulin consumption between baseline and 15 months.

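### The minimum Month 15 visit for completely withdrawn patients omits insulin dose and weight, so it may not yield IDAA1c or insulin consumption, two of the three key secondary endpoints

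*Protocol*

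**What the plan says.** Section 8.5 of the protocol distinguishes patients who stop study product but stay in follow-up from patients who withdraw completely. The second group is to be asked back at Month 15 so that follow-up is as full as it can be. The request is for a "preferable complete visit but as a minimum do the MMTT, C-peptide and HbA1c sampling, and collection of AEs". Table 2 footnote n repeats it ("Patients that have completely withdrawn from the study will be asked to return for a final visit at month 15") and points back to Section 8.5 for the detail.

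Section 6.4.2 names three key secondary endpoints. The first is "Change in insulin-dose-adjusted HbA1c (IDAA1c) between baseline and 15 months". The second is HbA1c on its own over the same interval, with no adjustment for dose. The third is "Change in daily exogenous insulin consumption between baseline and 15 months".

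Section 13.2.4 tests them in that order after the primary endpoint, in a fixed sequence at the 5% level. Section 13.2.3.2.1 analyses them with the same MMRM as the primary.

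Insulin dose is recorded per kilogram at Visit 2: "Insulin dose collected (Exogenous insulin dose/kg/24 hours) for 4 days prior to visit". Table 2 footnote i says: "Patients will record insulin dose in the eDiary for 4 days prior each visit starting from Visit 2". It adds that the Visit 2 dose is taken by the investigator into the eCRF. Weight is part of the general physical examination (Table 2, footnote e).

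**The concern.** The return visit exists to limit missing Month 15 data in patients who left the study. Its minimum covers the first and third tests in the hierarchy, but does not secure the data for the second and fourth.

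If a site applies the minimum as written, IDAA1c may rest on fewer Month 15 observations than the HbA1c from which it is built, with the shortfall confined to withdrawn patients. Nothing in the analysis plan could repair this later, because a dose and a weight that were not recorded at Month 15 cannot be recovered. The protocol gives no reason for keeping HbA1c and leaving out dose.

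**Working it through.** The point disputes no figure in the protocol. The main check compares the minimum visit with what each endpoint needs. The arithmetic only bounds the size.

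**1. What a minimum-only visit yields**

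| Endpoint (place in hierarchy) | Month 15 data needed | In the Section 8.5 minimum? |
|---|---|---|
| C-peptide AUC (1) | MMTT with C-peptide | Yes |
| IDAA1c (2) | HbA1c and insulin dose, with weight if dose is per kg | HbA1c only |
| HbA1c (3) | HbA1c | Yes |
| Daily insulin consumption (4) | Insulin dose, with weight if per kg | No |

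The protocol does not print the IDAA1c formula. That it needs insulin dose follows from its name. That it needs weight follows from the per-kilogram recording at Visit 2. Two other secondary endpoints in Section 6.4.2 are touched in the same way: the proportion with IDAA1c at or below 9, and the change in weight and BMI.

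**2. Whether another section fills the gap**
- Table 2 footnote n only refers back to Section 8.5.
- Section 8.4 asks for reasonable efforts to reach patients lost to follow-up and retrieve outstanding data. It names no items.
- Section 7.2 has patients enter doses in the eDiary for 4 days before each visit. Section 8.5 does not ask a patient who has left all evaluations to resume this. The Visit 7 list in Section 7.1.1.8 has an eDiary compliance check but no dose taken by the investigator.
- Section 11.1 keeps hypoglycaemia out of AE reporting unless it meets the SAE definition. Collecting AEs therefore misses severe episodes below that threshold, which the eCRF otherwise records separately (Table 2, footnote k).

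**3. Size**

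Inputs from Section 13.1: N = 106, including a 10% allowance for loss to follow-up. The total reproduces with the normal approximation if 0.134 is read as the difference between arms and 0.20 as the SD: 47 per arm; 47 / 0.90 = 52.2, rounded up to 53; 2 × 53 = 106.

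- Allowance: 0.10 × 106 = 10.6 patients, about 11.
- Remainder: 106 − 10.6 = 95.4 patients.

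Assumption: a share r of the 10.6 returns for the minimum only and gives neither dose nor weight. The protocol gives no value for r, so the full range is shown. The Month 15 count is 95.4 + 10.6 × r for C-peptide and HbA1c, and 95.4 for IDAA1c and insulin consumption. The standard-error ratio is the square root of the first count over the second.

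| r | C-peptide, HbA1c | IDAA1c, insulin | Gap | SE ratio |
|---|---|---|---|---|
| 0% | 95.4 | 95.4 | 0 | 1.000 |
| 25% | 98.05 | 95.4 | 2.65 | 1.014 |
| 50% | 100.7 | 95.4 | 5.3 | 1.027 |
| 100% | 106.0 | 95.4 | 10.6 | √(106 / 95.4) = 1.054 |

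The gap runs from 0 to about 11 patients, and the loss of precision from none to about 5%. These ratios count Month 15 observations only and give no credit for what the MMRM takes from earlier visits.

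**The case against.** The minimum is a floor, not the rule. Section 8.5 prefers a complete visit, and Table 2 includes dose, weight and severe hypoglycaemia at Visit 7. Patients who stop only the study product keep every visit. For someone who has left the study, a short list centred on the primary endpoint is a defensible choice, and nothing in the protocol contradicts it. All of this stands. It narrows the point to patients who return but decline the full visit, and those are the patients for whom a minimum is written.

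A reader might infer that IDAA1c and insulin consumption are certain to be lost for these patients. The document does not support that. Doses are ordinarily entered in the eDiary, and accounts are closed only at Visit 7 or later, so a dose may still arrive. Neither the dose entries nor the weight is required, however, so the accurate statement is that the data may be missing.

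A reader might also infer that the IDAA1c test is biased or more likely to fail, which would block the two tests after it. No direction of bias can be shown from the protocol, and blocking after a failure is a feature of any fixed sequence. Table 2 also schedules HbA1c and insulin dose at Visits 3 to 6. A withdrawn patient may therefore bring up to four post-baseline IDAA1c values into the MMRM before Month 15, against one MMTT (Visit 6) for the primary endpoint.

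Finally, the 10% in Section 13.1 allows for patients without an outcome. A patient who returns and completes the MMTT is not lost for the primary endpoint, so the allowance does not estimate the number of returners. It serves only as a rough ceiling.

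**Conclusion.** The gap is real and small. As written, a minimum-only return at Month 15 gives the primary endpoint and HbA1c, and does not secure IDAA1c, daily insulin consumption or the count of severe hypoglycaemia episodes that are not SAEs. With the 10% allowance taken as a rough ceiling, at most about 11 of 106 patients and about 5% in standard error are at stake. Reaching that ceiling would require every one of them to return, do only the minimum, and leave no usable dose or weight. The primary endpoint is unaffected.

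The case for acting is that this missingness is avoidable and falls on the first endpoint tested after the primary. It does not rest on any demonstrated error in the test. The conclusion assumes that IDAA1c is computed from HbA1c and insulin dose, and that dose is expressed per kilogram as at Visit 2. If insulin consumption were analysed in total units, weight would not be needed for that endpoint, but dose still would be.

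**What to change.** In Section 8.5 and in Table 2 footnote n, extend the Month 15 minimum for completely withdrawn patients by three items:
- insulin dose for the preceding 4 days, taken by the investigator into the eCRF as is already done at Visit 2
- body weight
- number of severe hypoglycaemia episodes since the last visit attended

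The collection method exists, and no new procedure or equipment is needed. The patient gives a few more minutes at a visit that already contains a 120-minute MMTT. The sponsor bears a small protocol amendment, handled under Section 14.1. The benefit is limited to patients who have not yet reached Month 15 when the change takes effect.
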